## 7.2. Analysis Sets

The following analysis sets are defined.

***Intent-to-treat analysis set – Propensity Score Selected (ITT-PS Selected):*** The ITT-PS Selected analysis set will include all subjects assigned to either the study or control groups in which treatment was attempted as defined by the recording of incision time. Subjects will be classified by the group in which they are assigned, regardless of whether or not that treatment was actually completed. Intraoperative failures will be included in primary non-inferiority testing as composite clinical endpoint failures. Primary efficacy analyses will be conducted using the ITT-PS Selected analysis set. A subject must be selected into a PS subclass in order to be included in analyses. The PS subclassification procedure is designed to retain all subjects receiving the study device, if possible. Since selection into a PS subclass is the observational study equivalent to randomization in a randomized study, control subjects not selected into a PS subclass will not be included in the ITT-PS Selected analysis set and not included in primary effectiveness and safety analyses. Safety data will be summarized separately for trimmed controls.

***Completers Analysis Sets:*** Completers analysis sets will be defined at ITT-PS Selected evaluable for composite clinical success.

***Safety analysis set:*** The Safety analysis set will include all subjects in the ITT-PS Selected analysis set plus study device patients who were not selected into a PS subclass, if any. Study device patients who were not selected into a PS subclass will be assigned to the subclass with the largest propensity scores for analyses that control for PS. Primary safety analyses will be conducted using the Safety analysis set.

***Per Protocol analysis set (PP):*** The PP analysis set will include subjects in the ITT-PS Selected analysis set with no major protocol violations of inclusion or exclusion criteria, as determined by the Clinical Events Committee (CEC) and who are evaluable for the Month 24 composite clinical success endpoint (Objective 2, 3, and 4) or evaluable for the Month 60 CCS (Objective 1). It may also exclude subjects with confounding medical events or treatments following index surgery that are expected bias determination of the primary composite clinical success endpoint, as determined by the CEC. Secondary efficacy analyses will be conducted using the PP analysis set.

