#### 7.6. Objective 4: Real Conditions of Use

Coflex device performance will be evaluated in a “real conditions of use” study by testing the hypothesis that device performance is not clinically inferior in the PAS population relative to device performance defined by IDE study results. Patients will be enrolled from sites that were not involved in the IDE study. The same Month 24 composite clinical success (CCS) endpoint used in the IDE trial will be used in analyses to facilitate this comparison.

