**Ho:  $CCS_{PAS} \leq 0.662 - 0.10 = -0.562$  (inferior)**

**Ha:  $CCS_{PAS} > 0.662 - 0.10 = -0.562$  (not inferior).**

**Non-inferiority will be concluded if the posterior probability is at least equal to 0.95.**

If the inferiority hypothesis is rejected, then the numbers of coflex® successes and failures observed in the PAS will be used to update the Bayesian posterior probabilities of non-inferiority and superiority relative to fusion that were first established in the IDE study and reported in the coflex® SSED. This will facilitate a formal accumulation and summary of what has been learned about the relative effectiveness of coflex® compared to fusion based on pooling relevant information from the IDE trial and this PAS. As reported in the coflex® SSED, the Bayesian posterior probability that coflex® is not clinically inferior to fusion ( $\delta=-0.10$ ) is 0.999362. Similarly, the Bayesian posterior probability that coflex® is superior to fusion in terms of Month 24 CCS was reported to be equal to 0.927550.

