#### **7.7.4. Objective 4: Real Conditions of Use**

Non-informative priors were assumed for the both comparisons groups, since IDE results cannot be used as the basis of an informative prior if the comparison is to be made to that same IDE trial. However, the Bayesian simulation R function was modified to reflect that it is known that exactly 135 successes were observed among 204 evaluable patients in the coflex IDE analysis set (see Simulation Report, Section 8.3). Otherwise, all other features of the Bayesian simulation were kept the same.

A design was identified that uses a non-inferiority margin of -0.1175 and a 0.95 posterior probability threshold. This design has an estimated type 1 error of 0.045 and power of about 80%. Other assumptions include expected success rates 0.662 in both groups when determining power and assuming that the Month 24 success rate in the PAS population is 0.10 smaller than in the IDE study population for evaluating type 1 error.

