## 7.11. Handling of Missing Data for Primary CCS Endpoints

### 7.11.1. Bayesian Multiple Imputation

To best preserve an intent-to-treat analysis, the testing of the primary Month 60 superiority hypothesis (Objective 1) will be done on the ITT-PS selected analysis set. Those subjects who withdraw, or who are lost to follow-up (LT FU) after enrollment will be included in the analysis using a modification of Bayesian multiple imputation to accommodate the PS subclass design. This analysis will be the primary analysis, but recognizing that there is no way, statistically, to handle these subjects without possibly introducing bias, a tipping point analysis will be also be conducted. For comparison purposes, a completers analysis will also be performed. The following describes the method. A similar method will be applied to analyses for other objectives.

In general, Bayesian Multiple Imputation (MI) may be employed to impute the expected status at Month 60 for patients who have not completed follow-up and have not been identified as “terminal failures”. Terminal failures include any event which is counted as a CCS failure no matter what happens after such an event occurs such as a secondary surgical invention. The imputation algorithm uses a beta-binomial distribution to model the transition probabilities from the outcome at month  $j$  to that at month 60, separately for the treatment and control groups. Specifically, the probability of a success for a subject in treatment group  $t$ , with last follow-up  $j$  and last follow-up value  $r$  can be described using a beta distribution:

$$\Pi_{p,t,j,r} \sim \beta(1 + S_{p,t,j,r}, 1 + F_{p,t,j,r})$$

Where  $p$  = propensity score subclass = {1, 2, 3, 4, 5}

$t$  = treatment group = {coflex=S, Decompression=D}

$j$  = follow-up time = {3, 6, 12, 24, 36, 48}

$r$  = success or failure status at time  $j$  = {1=success, 0=failure}

$\Pi_{p,t,j,r}$  = Month 60 success probability for subjects in subclass  $p$ , in treatment group  $t$ , who were successes ( $r=1$ ) or failures ( $r=0$ ) at follow-up time  $j$ .

$S_{p,t,j,r}$  = Number of Month 60 successes for subjects in subclass  $p$ , in treatment group  $t$ , who were successes ( $r=1$ ) or failures ( $r=0$ ) at follow-up time  $j$ .

 Guidance for Industry and FDA Staff Clinical Data Presentations for Orthopedic Device Applications Document issued on: December 2, 2004.

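### Objective 4 inherits the propensity-score-selected analysis set, and the plan does not settle whether its counts are crude or PS-adjusted, although decompression controls play no part in that comparison

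*Combined protocol and SAP*

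**What the plan says.** **Target.** Section 7.6 tests whether "device performance is not clinically inferior in the PAS population relative to device performance defined by IDE study results". The comparator is the IDE coflex result, and no decompression data enter.

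**Analysis set.** Sections 4.12 and 7.2 assign primary efficacy analyses to ITT-PS Selected. Section 7.2 states: "A subject must be selected into a PS subclass in order to be included in analyses". Neither section makes an exception for Objective 4. The Per Protocol set is a subset of ITT-PS Selected, and its definition names Objective 4 among those it serves: subjects must be "evaluable for the Month 24 composite clinical success endpoint (Objective 2, 3, and 4".

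**Trimming.** Section 7.17.1 trims from the extremes of the propensity score distribution. It first forces all device patients to be kept. Only if the balance criteria then fail does it remove a very small number, whose effectiveness is summarized separately and compared with the primary set. Sections 4.12, 7.2 and 7.17.1 place unselected device patients in the highest-score subclass for safety analyses.

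**Counts.** Section 7.1 averages the five subclass success rates with equal weight in each group and multiplies by the group size to get adjusted successes and failures. Section 7.11.1 builds imputation and adjusted totals on the same subclasses for Objective 1, then says: "A similar method will be applied to analyses for other objectives". Section 7.6 refers to the coflex successes and failures observed in the PAS, for the later update against fusion. Section 7.7.4 describes a separate Objective 4 simulation and mentions no PS adjustment.

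**The concern.** Propensity score selection exists to make coflex and decompression patients comparable. Objective 4 makes no such comparison. Overlap with decompression controls is therefore not a reason to keep or drop a coflex patient from a test of how the device performs in use. Losses would not be random either, because trimming works at the extremes of the score and the plan expects unselected device patients to belong with the highest scores.

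The counts raise a related question. Equal weighting of subclasses is justified in section 7.1 as part of estimating an average treatment effect between two groups. Applied to a single arm, it gives the success rate for an even mix of subclasses. That equals the rate among the coflex patients treated only when they are evenly spread over subclasses or when success does not vary across them. The sizing rests on a simple binomial count, so an adjusted count would not have exactly the stated operating characteristics. What is at stake is the pass or fail of Objective 4 when the result is near the cut-off.

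**Working it through.** **Inputs from the plan (section 7.7.4 unless noted)**
- Comparator: "exactly 135 successes were observed among 204 evaluable patients in the coflex IDE analysis set".
- Priors: "Non-informative priors were assumed for the both comparisons groups". I use beta(0.5, 0.5); beta(1, 1) gives the same cut-off.
- Rule: "A design was identified that uses a non-inferiority margin of -0.1175 and a 0.95 posterior probability threshold".
- Rates: 0.662 for power; 0.10 lower, that is 0.562, for type 1 error.
- Evaluable coflex n: 150 (section 7.7.2). It is not restated for Objective 4, but the other simulation features were kept the same.
- Enrolment: 15% loss and a 5% coflex trimming allowance (section 4.2). 150 / 0.85 / 0.95 = 185.8, hence 186.

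**Step 1: reproduce the stated design with crude counts**

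For x successes in 150, compare beta(0.5 + x, 150.5 − x) with beta(135.5, 69.5) and find P(p_PAS − p_IDE > −0.1175).

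| x of 150 | Posterior probability | Result |
|---|---|---|
| 93 | 0.929 | fail |
| 94 | 0.945 | fail |
| 95 | 0.959 | pass |
| 96 | 0.969 | pass |

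The cut-off is 95.
- Power = P(Bin(150, 0.662) ≥ 95) = 0.797. The plan states about 80%.
- Type 1 error = P(Bin(150, 0.562) ≥ 95) = 0.0458. The plan states 0.045.

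The documented design is thus reproduced by a plain binomial without PS adjustment.

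**Step 2: effect of trimming (assumed inputs)**

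If a fraction f of coflex patients is trimmed and their success rate is d points below that of the retained patients, the retained rate exceeds the full coflex rate by f × d.
- f = 1%, d = 10: 0.1 point.
- f = 5%, d = 40: 2.0 points.
- f = 0: no shift.

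With a true coflex rate of 0.562 and the cut-off at 95/150:

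| Upward shift | Type 1 error |
|---|---|
| 0 | 0.046 |
| 1 point | 0.075 |
| 2 points | 0.116 |

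If trimmed patients do better than the rest, the shift is downward and power falls instead: a 1-point downward shift takes it from 0.797 to 0.716.

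**Step 3: effect of equal weighting, if it is used (assumed inputs)**

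Shift = coflex-weighted rate − equal-weighted rate = Σ nᵢrᵢ / 150, where rᵢ is the subclass rate measured from the middle subclass.

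- 30 per subclass: 0, so adjusted and crude counts are identical.
- 24/27/30/33/36, rates −5 to +5 in steps of 2.5: (−120 − 67.5 + 0 + 82.5 + 180) / 150 = 0.5 point.
- 18/24/30/36/42, rates −10 to +10 in steps of 5: (−180 − 120 + 0 + 180 + 420) / 150 = 2.0 points.
- 15/22/30/38/45, steps of 2.5: (−75 − 55 + 0 + 95 + 225) / 150 = 1.3 points. Steps of 5 double this to 2.5 points.

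Simulated operating characteristics (400,000 trials each; adjusted counts need not be whole numbers, so their cut-off is 94.3):

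| Coflex split | Spread of rates | Adjusted estimate moves | Type 1 error | Power |
|---|---|---|---|---|
| 24/27/30/33/36 | 10 points | −0.5 | 0.039 | 76% |
| 24/27/30/33/36 | 10 points, reversed | +0.5 | 0.064 | 84% |
| 18/24/30/36/42 | 20 points | −2.0 | 0.020 | 63% |
| 18/24/30/36/42 | 20 points, reversed | +2.0 | 0.129 | 91% |

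Uneven subclasses also cost precision. For 18/24/30/36/42 the effective n is 25 / Σ(1/nᵢ) = 25 / 0.182 = 137, yet the adjusted counts are entered as if n were 150.

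**Step 4: operating characteristics after the fix**

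Crude counts at n = 150 return Step 1. If nobody is trimmed and 15% are lost, n is 186 × 0.85 = 158: cut-off 100, power 80.5%, type 1 error 0.042.

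**The case against.** The plan limits the problem. Device patients are kept if possible, at most a very small number may be trimmed, and their results are reported and compared separately. If none is trimmed, ITT-PS Selected already contains every coflex patient with an incision. The 5% is a sample-size allowance, not a forecast that about 9 patients will be lost. Sites are chosen for comparable patient mix, and section 7.1 expects roughly equal numbers of the two groups within subclasses. The splits and gradients above come from no document. All of this stands, and it is why the effect can be zero. It does not close the gap: a separate summary does not return a trimmed patient to the hypothesis test, and it does not say which counts enter it.

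A reader might go further and infer that Objective 4 will be estimated with PS-adjusted counts for the wrong population. The documents do not support that. No sentence says adjusted counts enter the Objective 4 test. Section 7.1 is written for the non-randomized group comparison, and section 7.11.1 promises only a similar method. Section 7.6 speaks of observed counts, although for the fusion update, and the sizing in section 7.7.4 matches a plain binomial. Nor do the documents show that trimmed coflex patients would be the most typical users: no coflex score distribution is given, and extreme scores need not be typical.

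A reader might also want PS subclasses banned from the Objective 4 imputation. Imputing within subclass conditions on baseline covariates and does not by itself change the target population, so a ban would be a preference, not a correction.

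**Conclusion.** The concern holds in a limited form. By the plan's stated rule, any coflex patient trimmed for poor overlap with decompression controls is excluded from the PAS-versus-IDE test, where that overlap is irrelevant. Whether the test uses crude or equal-weighted counts is left open, with the general sections pointing one way and the Objective 4 sections the other.

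The size cannot be known in advance. It is zero with no coflex trimming and an even spread over subclasses. Under the assumed skews, equal weighting moves the rate by about 0.5 to 2.5 points in either direction; the assumed trimming cases give 0.1 to 2.0 points. A shift of 2 to 4 patients in 150 decides the result only near the cut-off of 95.

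These figures use the −0.1175 margin. Section 7.6 instead prints a bound of "0.662 - 0.10 = -0.562", which is a separate inconsistency and does not affect this point.

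**What to change.** In sections 4.12, 7.2 and 7.6, state that the primary Objective 4 analysis includes all coflex patients with a recorded incision, including any trimmed in the PS step. State that it uses unweighted numbers of successes and failures, with imputed values included. Keep the PS-selected, PS-adjusted version as a sensitivity analysis.

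Subclass-based imputation can stay. Trimmed device patients only need a subclass for it, and the plan's existing safety rule (the highest-score subclass) can be extended to this use.

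The cost is SAP wording and one additional analysis set. No new patients or data are needed, and the documented power and type 1 error are preserved.

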	
 
• Change from baseline to Month 24 and Month 60 in maximum walking time from treadmill test as a continuous variable and in terms of achieving at least an 8 minute improvement or maximum time of 15 minutes.
 
• Change from baseline to Month 24 and Month 60 in time to symptoms from treadmill test as a continuous variable and in terms of achieving at least an 8 minute improvement or maximum time of 15 minutes.
 
• Neurological status (motor, sensory, reflex, SLR - assessment of maintenance of improvement after surgery throughout study duration).
 
• Radiography Endpoints 
 
1. Assessment of significant migration of the implant or the complete expulsion (significant is defined > 5 mm).
 
2. Assessment of spinous process fracture.
 
3. Assessment of maintenance of foraminal height
 
4. Assessment of adjacent level disease determined by independent radiographic review
 
 
 
• Correlation of foraminal height changes to improvement of walking distance on a treadmill (after 24 and 60 months compared to baseline).
 
• The CCS will be modified to examine the effect narcotics use (opioids and/or opiates) has on treatment success rates. When comparing coflex® in conjunction with decompression to decompression alone, this modified Month 24 CCS will include: 
 
• No “Treatment Failure” on or before the exact 2-year anniversary of the index surgery. Treatment Failure will include: 
 
1. No surgical intervention at the index level
 
2. No lumbar epidural steroid injection including nerve root blocks and facet blocks at any lumbar level
 
 
 
• No persistent new or worsening sensory or motor deficit where persistence is established by identifying new or worsening deficits at Month 18 that do not resolve by Month 24.
 
• No major device-related adverse event defined as an event simultaneously both ‘Serious’ and ‘Definitely’ according to independent Clinical Events Committee (CEC) related to the implant on or before the exact surgical two-year anniversary or exact five-year anniversary. In the decompression alone group, since there is no device, this endpoint will be identified as any serious AE that is classified as definitely related to surgery.
 
 
 

--	--

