### **3.2.1. Discussion about Month 60 Composite Clinical Success (CCS)**

After careful consideration, handling of lumbar injections will differ between the Month 24 CCS and CCS endpoints determined post Month 24, and in particular, for the primary Month 60 CCS to be used in Objective 1 analyses. As with the IDE study, lumbar injections that occur prior to two years post operatively are defined as Terminal Treatment Failures, Month 24 composite clinical failures and further follow-up is censored when summarizing effectiveness endpoints (i.e., ODI, VAS, ZCQ, treadmill). This is designed to (1) produce a composite endpoint that is sensitive to early device failure and to (2) avoid bias arising from inclusion of clinical data that could be reflecting successful secondary treatment of a failed index treatment. A different approach seems advisable for the Month 60 CCS endpoint for use in this ‘real conditions of use’ study. The goal is to avoid classifying calling transient symptom management as a device failure unless there is subsequent re-operation or unless patient status is compromised as reflected in lack of an ODI improvement from baseline that is less than 15%. Therefore, for Month 60 CCS, lumbar injections occurring within 12 months of the Month 60 visit will indicate Month 60 CCS failure (as well as those within the first 24 months post-surgery). This is because a lumbar injection within 12 months of the Month 60 visit can confound the Month 60 assessment. Similarly, when determining intermediate CCS at Month 36 and Month 48, lumbar injections within 12 months of these clinic visits will indicate CCS failure for that time point, but not necessarily for subsequent time points. However, patients with 2 or more series of injections will be defined at terminal failures, that is, as a CCS failure at that time point and all subsequent timepoints.

As noted above, handling of lumbar injections will differ between the Month 24 CCS and CCS endpoints determined post Month 24, and in particular, for the primary Month 60 CCS to be used in Objective 1 analyses. In sensitivity analysis, lumbar injections occurring at any time between surgery and Month 60 will be considered a treatment failure. All other endpoints in the Month 60 CCS analysis remain identical in the sensitivity analyses.

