### 3.3. Secondary Endpoints

- ODI change compared to baseline at 24 and 60 months as a continuous variables and in terms of achieving at least a 15 point improvement.
- Change in Visual Analog Scale (VAS) for low back pain (on the 100 mm scale) after 24 and 60 months compared to baseline as a continuous variables and in terms of achieving a 20 point improvement.
- Change in right and left leg pain using a Visual Analog Scale (VAS) 100 mm scale after 24 and 60 months compared to baseline as a continuous variable and in terms of achieving a 20 point improvement. A separate analysis will be performed to compare VAS scores for the “worst” legs.
- Change of Zurich Claudication Questionnaire (ZCQ) after 24 and 60 months compared to baseline:
  - Symptom severity (range 1-5)
  - Physical function (range 1-4)
  - Patient satisfaction (range 1-4, no baseline).
  - ZCQ Overall Success ( $\geq 2$  of 3 of the following)
    - Improvement in symptom severity  $\geq 0.5$
    - Improvement in physical function  $\geq 0.5$
    - Satisfied or somewhat satisfied as defined by a score of  $\leq 2.5$  points on the patient satisfaction domain.
  - ZCQ Overall Success components
- Maintenance or improvement in EQ-5D compared to baseline
- Change from baseline to Month 24 and Month 60 in maximum walking time from treadmill test as a continuous variable and in terms of achieving at least an 8 minute improvement or maximum time of 15 minutes.
- Change from baseline to Month 24 and Month 60 in time to symptoms from treadmill test as a continuous variable and in terms of achieving at least an 8 minute improvement or maximum time of 15 minutes.
- Neurological status (no new or worsening, persistent neurological deficit)
- Radiography Endpoints
  - Assessment of significant migration of the implant or the complete expulsion (significant is defined  $> 5$  mm).
  - Assessment of spinous process fracture.
  - Assessment of maintenance of foraminal height
  - Assessment of adjacent level disease determined by independent radiographic review
- Correlation of foraminal height changes to improvement of walking distance on a treadmill (after 24 and 60 months compared to baseline).

 Pratt RK et al., The Reliability of the Shuttle Walking Test, the Swiss Spinal Stenosis Questionnaire, the Oxford Spinal Stenosis Score and the Oswestry Disability Index in the Assessment of Patients with Lumbar Spinal Stenosis. Spine Vol. 27 (1) pp. 84-91.

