#### **4.8.10. Schedule of Study Visits**

A tabular summary of visit schedule is provided below.

Visits	Screening		Follow-Up						Final Report
	1 < 4 weeks before d0	2 day 0 surgery	3 months after surgery (±2 weeks)	4 12 months after surgery (±2 month)	5 24 months after surgery (±2 month)	6 36 months after surgery (±4 months)	7 48 months after surgery (±4 months)	8 60 months after surgery (±4 months)	
Patient information and Informed consent	X								
Demographics	X								
Medical history	X								
Pain management	X	X 	X	X	X	X	X	X	
Physical examination	X 		X 	X 	X 	X 	X 	X 	
Neurological status	X	X 	X	X	X	X	X	X	
Inclusion/exclusion criteria	X	(X)							
X-ray in standing position (AP, lateral, flexion, extension)	X	X 	X	X	X 	X	X	X 	
MRI and/or Post Myelo CT (not older than 6 months)	X								
Diagnosis	X								
Walking Distance Test (treadmill)	X		X	X	X	X	X	X	
VAS back pain, VAS leg pain	X		X	X	X			X	
ODI, ZCQ, EQ-5D	X		X	X	X	X	X	X	
Surgery		X							
Patient's satisfaction questionnaire			X	X	X	X	X	X	
Documentation of AEs		X	X	X	X	X	X	X	

1) A detailed physical examination will be performed at visit 1. In the following visits only a routine physical examination will be performed and changes compared to screening will be recorded. The investigator is free to perform a complete physical examination.

2) Only group B (with coflex® implant: anterior-posterior, lateral).

3) After surgery, before discharge.

4) CT Scans will be conducted at 24 months for all subjects and at 60 months for all symptomatic, confirmed spinous process fracture subjects.

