## 6.7. Documentation of Adverse Events

New or worsening AEs will only be documented for each patient until the last study related patient visit.

The investigator will assess and record any AE in detail on the 'AE' form included in the case report forms (eCRFs).

Investigators will actively check for and report potential device- or procedure- related Adverse Events for all study patients in the time period between the first device application and the end of the clinical phase of the trial at the site.

Investigators will also report to the CRA all unexpected (i.e., not listed in Section 6.1) and Serious Adverse Events (see Section 6.4 for contact information) by completing the Adverse Event eCRF in the EDC. The CRA will forward this report to the sponsor. The sponsor will then make an evaluation if he agrees that the unexpected and serious AE was in fact device- or procedure-related. It is the reporting responsibility of the Investigator to notify the responsible IRB of Adverse Events which are classified by the sponsor as serious, unexpected and related, unless otherwise required and documented by the IRB.

All AEs must be recorded and followed up until the event is either resolved or adequately explained, even after the patient has completed the clinical investigation.

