### **7.9. Analysis of Secondary Effectiveness Endpoints**

Secondary continuous effectiveness endpoints will be summarized by treatment group over time and as changes over time with descriptive statistics including means, standard deviations,

median, minimum and maximum values. Secondary categorical effectiveness endpoints will be summarized by treatment group over time using counts and percentages. Descriptive effect size measures such as mean differences and differences in percentages responding will be provided with 95% confidence intervals or 95% credible intervals as an aid in evaluating the likely ranges of true treatment group differences.

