

eliminate systematic biases in treatment-control comparisons (Rubin 2008). Moreover, the "propensity score technique allows the straightforward assessment [of] whether the treatment groups overlap enough regarding baseline covariates to allow for a sensible treatment comparison" (Yue 2007).

The PS sub classes will be formed when the prospective enrollment is completed. As part of the modeling process it typically is necessary to iteratively trim subjects from the extremes of the PS distributions in order for the Imbens and Rubin 2015 PS model estimation validity criteria to be met. For regulatory studies, the heuristic has been modified to initially force retention of all investigational device subjects. If it is not possible to meet the optimality criteria when retaining all study device subjects, only then will we sequentially trim a (very) small number of investigational patients in an attempt to satisfy the optimality criteria. These processes will all be detailed in a PS Results Memorandum that will be submitted to FDA for review prior to unblinding of the outcomes-blinded statistician responsible for identifying the optimal PS subclassification. In the event it is necessary to exclude any investigational device subjects, effectiveness results for these subjects will be summarized separately, and compared to those in the primary analysis set, and the potential implications of excluding patients discussed in the PMA. These patients will, however, be included in all safety analyses. In safety comparisons that adjust for PS subclass, excluded study device patients will be included in the quintile with the highest propensity scores. Non-selected control patients will not be included in efficacy analyses. Safety events for non-included controls will be listed separately.

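### Core-lab implant migration, expulsion and spinous process fracture fall under the per-protocol rule for secondary efficacy, so findings not recorded as adverse events may be missed in patients outside that set

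*Combined protocol and SAP*

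**What the plan says.** The Synopsis and sections 3.3 and 5.2 place the radiographic findings among the secondary effectiveness criteria: "Assessment of significant migration of the implant or the complete expulsion" (threshold 5 mm) and "Assessment of spinous process fracture". All films are read centrally (4.7.7, 5.2.6, 5.2.7).

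Sections 4.12 and 7.2 give the rule for the analysis set: "Secondary efficacy analyses will be conducted using the PP analysis set". PP requires evaluability for the Month 24 or Month 60 composite clinical success (CCS) endpoint and no major eligibility violation. The CEC may also remove patients whose later events or treatments it expects to bias the composite. Section 7.9 promises that "Secondary categorical effectiveness endpoints will be summarized by treatment group over time using counts and percentages" but names no set.

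On safety, section 6.1 lists spinous process fracture and an implant that moves or breaks as anticipated adverse events (AEs). Section 7.18.1 bases the safety assessment on AEs, and primary safety analyses use the Safety set. Section 6.7 adds: "Investigators will actively check for and report potential device- or procedure- related Adverse Events for all study patients". For device patients trimmed in the propensity score design, section 7.17.1 says "effectiveness results for these subjects will be summarized separately, and compared to those in the primary analysis set" and keeps them in all safety analyses.

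**The concern.** PP restrictions suit a sensitivity analysis of the composite. They do not suit a count of displaced implants or fractures. A patient enrolled despite an excluding bone-density score may have complete films, and bone quality is plausibly relevant to fracture, yet that patient is outside PP. A patient lost before the composite can be assessed may already have films showing migration.

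The AE route does not fully close this. Section 6.1 describes AEs as reported by the patient or observed by the investigator and does not name the core lab. The CEC reviews AE reports (7.19), so a finding never entered as an AE does not reach it. The plan implies that silent fractures can occur: every patient has a Month 24 CT, but CT is repeated "at 60 months for all symptomatic, confirmed spinous process fracture subjects", and section 5.2.7 says a fracture is not a treatment failure. A fracture alone therefore does not make a lost patient evaluable for the composite.

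At stake is the completeness of device-integrity reporting in an FDA-mandated real-conditions-of-use study.

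**Working it through.** **1. Which findings already have a reporting route**

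| Situation | Route in the plan | Gap? |
|---|---|---|
| Recorded as an AE | Safety set (6.1, 7.2, 7.18.1) | No |
| Device patient trimmed by propensity score | Separate effectiveness summary; all safety analyses (7.17.1) | No |
| Implant revised or removed | Treatment failure (5.1.2), so normally evaluable | No, unless the CEC excludes the patient |
| Core-lab finding, no AE, patient in PP | Secondary endpoint tables | No |
| Core-lab finding, no AE, patient outside PP | None stated if the PP rule is applied literally | Yes |

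**2. Scale from the plan's allowances.** Inputs from section 4.2: 150 per group, 15% loss, trimming of 5% (coflex) and 20% (control). The stated enrolment reproduces:
- Coflex: 150 / (0.85 × 0.95) = 185.8, stated 186.
- Control: 150 / (0.85 × 0.80) = 220.6, stated 220.

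Loss among coflex patients: 186 × 0.15 = 27.9, about 28. If 5% are trimmed first, 186 × 0.95 × 0.15 = 26.5. The documents give no number for eligibility violators or CEC exclusions.

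**3. Films held by lost patients (illustration).** Assume the 27.9 are lost evenly over 60 months, and that a patient lost before Month 24 is not evaluable unless already a failure. Losses per interval are 1.4 (Months 0–3), 4.2 (3–12), and 5.6 in each of the four later 12-month intervals. Planned follow-up X-ray sets: 186 × 6 = 1,116.
- Lost before Month 24, in neither PP set: 4.2 × 1 + 5.6 × 2 = about 15.3 sets, or 1.4% of 1,116.
- Lost after Month 36, in the Month 24 PP set only: 5.6 × 1 + 5.6 × 2 = about 16.7 Month 36 and 48 sets. These are outside only if those films follow the Month 60 PP set, which the plan does not say.
- Both together: about 32 sets, or 2.9%.

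Section 5.2.6 omits Month 12 from the migration readings, although 4.7.2 and 4.8.10 schedule those X-rays. Without Month 12, the first count falls to 4.2 + 5.6 = 9.8 sets for migration.

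**4. Effect on a reported rate (illustration).** The documents give no event rate. Let p be the Month 60 rate in kept patients and r the hazard ratio of lost to kept patients. Assume a constant hazard and all loss after Month 48. The all-readings cumulative incidence is then

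1 − [0.85 q^0.8 + 0.15 q^(0.8r)] × q^0.2, with q = 1 − p.

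- p = 0.10, r = 1/3: 9.22%
- p = 0.10, r = 1: 10.00%
- p = 0.10, r = 3: 12.09%
- p = 0.20, r = 3: 23.6%

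The shift is zero at r = 1, takes either sign, and grows with p. It covers all findings, including those that reach the Safety set as AEs, so for a given p it overstates the gap at issue.

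**The case against.** The strongest reply is that PP was never meant to govern these endpoints. The PP sentence parallels the one assigning primary efficacy analyses to the ITT-PS Selected set, and PP is defined by composite evaluability for each objective. It can fairly be read as meaning supportive analyses of the composite. Section 3.2.1 points the same way: "further follow-up is censored when summarizing effectiveness endpoints (i.e., ODI, VAS, ZCQ, treadmill" lists no radiographs. This stands as a possible reading. It leaves the radiographic endpoints with no named set, which still needs a sentence.

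A second reply is that core-lab results probably return to sites. The Month 60 CT depends on core-lab confirmation, sites hold the films, and investigators must look for device-related AEs. This also narrows the gap. The text supplied states no rule for entering a core-lab reading as an AE. The case report forms and Radiographic Protocol (Appendices I and V) are not reproduced and may contain one.

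A reader might infer that the plan keeps these harms out of safety reporting altogether. It does not: section 6.1 lists them as anticipated AEs. Nor are trimmed device patients lost from view, given section 7.17.1.

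**Conclusion.** The point holds in limited form. Read literally, the only set rule that reaches core-lab migration, expulsion and fracture is PP, and no provision assigns the core-lab readings themselves to the Safety set. The exposed cases are findings not recorded as AEs in eligibility violators, CEC-excluded patients and patients not evaluable for CCS.

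The size cannot be determined. Roughly 28 of 186 coflex patients follows from the planning allowance for loss and is not an upper bound, because violators and CEC exclusions add to it. It might be tempting to conclude that a reported rate could move by no more than about 2 points. The documents do not support that: the figure depends on an assumed 10% rate, and an assumed 20% rate gives a shift of 3.6 points (23.6% against 20%). The direction is also unknown.

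No primary objective or composite conclusion is affected. Confidence is medium, because the appendices are unseen and the PP sentence has a second reading.

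**What to change.** State in sections 4.12/7.2 and 7.18 that core-lab migration, expulsion and spinous process fracture are tabulated in the Safety analysis set, from all available readings, whether or not recorded as AEs. Show the number of patients read at each visit. Keep any PP table as supplementary. Cumulative incidence to Months 24 and 60 would be a useful format, but that is a preference; the essential change is the denominator.

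This is a cheap improvement: a short SAP statement and one extra table from films already collected and read, with no new visits or images. The downside is the extra table and possibly slightly less favourable harm rates.
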